**Overview of the study.** We will determine the effects of HAI on reducing anxiety, depression, worry, and pain and enhancing QoL in children (n=30) (ages 8-17 years) with a LTC and their parent caregivers (n = 30-60). Human-animal interactions will involve visits from a registered canine team for 10-15 minutes during each child's potentially anxiety-producing appointments at the clinic or hospital. These appointments occur approximately once/week: Children and parent dyads will receive HAI intervention and complete measures of anxiety, depression, worry, pain and QoL at baseline, 4 weeks and at the end of the study (8 weeks).

**Eligibility Criteria and Recruitment.** Our sample target is 30 children diagnosed with advanced cancer and their parents/guardians. We will oversample to conservatively accommodate a drop-out of up to 35%, thus our accrual target sample is 48 children and parent/guardian pairs. Inclusion criteria for children are: 1) ages of 8-17 years, 2) diagnosed with advanced cancer as defined by any stage of relapsed, recurrent or refractory cancer as indicated by healthcare team and 3) able to understand English or Spanish to complete consents and surveys. Inclusion criteria for caregivers are: 1) parent or guardian as determined by person who brings child to >50% of their clinic visits, and 2) able to understand English or Spanish to complete consents and surveys. Inclusion criteria for animal therapy teams are: 1) registered Pet Partners or other nationally recognized agency team, 2) owner able to speak and understand English or Spanish, 3) owner who has successfully completed volunteer training at Vanderbilt University Medical Center.

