**Table 1. Estimates of Children Meeting Inclusion Criteria and Recruitment Rates**

Children Ages 8-17 Years with Advanced Cancer at MCJCHV	Total Per Year	Total 18 Months
Number of eligible participants per year	32	48
T1: Accrual (96% in previous studies, conservative estimate for this population is 85%)	27	40
End of Study: Retention (95% in previous studies, but conservative estimate for this population is 75%)	20	30

**Setting.** All study activities including procedures and data collection will take place in the treatment room in the hematology/oncology clinic or a private room at MCJCHV and will occur approximately weekly. Sessions will coincide with children and families' scheduled medical appointments or inpatient hospitalizations.

**Procedures.** After potential participant families are identified and screened for inclusion/exclusion criteria, the PI or project coordinator will meet with the primary caregiver, introduce the study, and review the IRB-approved consent. If the parent/guardian agrees, the child will be approached for assent. Participants will then be asked to complete baseline measures. Human-Animal Interactions will occur at each clinic visit or hospitalization, as long as they are not more frequent than weekly. Data collection will occur at baseline, 4 weeks, and study end (8 weeks) with children and parents completing surveys in private sections of the room. All study data will be stored in REDCap, a secure, web-based application for building and managing databases. Tablets will be used by study participants to enter their responses to study measures into their study record in REDCap. Paper forms will be available to participants if there is a problem with network connectivity or if the participant prefers that form. Subsequently, data on paper forms will be double-entered into the participant's record in REDCap by trained study staff and verified.

**Human-Animal Interactions (HAI).** Every effort will be made to ensure the same dog is used consistently with each family, but a back-up team will be available in the event the HAI team is ill or unavailable. The HAI consists of the following: 1) *Social Interaction*: participants will be guided by the canine owner in interfacing with

Version approved by IRB 11-18-2019

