**Table 2. Measures and Schedule**

Variable	Measure	# items/Scoring Range Clinical Significance	Time to Complete	Schedule
AIM 1			Minutes	
Safety/Feasibility	AAT Activity Log	22 items	5	After each HAI
Feasibility	Recruitment Rate, Attrition			Consent/assent. After final HAI
Intervention	Videotaping of All Sessions		15	During each HAI
AIM 2				
Anxiety – Trait	State-Trait Anxiety Inventory for Children (STAIC) Trait Form	20 items/20-80; Clinical significance 39-40	5	Baseline
Anxiety – State	STAIC State Form	20 items/20-80; Clinical significance 39-40	5	Baseline, 4 & 8 wks
QoL	PedsQL-General	23 items/range 0-92	15	Baseline, 4 & 8 wks
	Peds QL-Cancer	27 items/range 0-108		Baseline, 4 & 8 wks
HR and B/P	Heart Rate and B/P Log		2	Baseline, 4 & 8 wks
Depression	PROMIS Depressive Symptoms	8 items	2	Baseline, 4 & 8 wks
Acute Stress	Salivary Cortisol		3	Baseline, 4 & 8 wks
	Urinary NE, creatinine		20	Baseline 4 & 8 wks
HAI Perceptions	Open-Ended Interview	Semi-Structured	15	End of Study
	Parent Family Demographic Form	14 items	10	Baseline
Child QoL	PedsQL General and Cancer-Parent Proxy	26 items	5	Baseline, 4 & 8 wks
Anxiety – Trait	STAI – Trait Form (Adult)	20 items/20-80; Clinical significance 39-40	5	Baseline
Anxiety – State	STAI –State Form (Adult)	20 items/20-80; Clinical significance 39-40	5	Baseline, 4 & 8 wks
Depression	PROMIS Depressive Symptoms Parent Proxy	6 items	2	Baseline, 4 & 8 wks
HAI Perceptions	Open Ended Interview		15	End of Study

**Data Management.** [name] (Co-I, VUSN biostatistician) will provide support for: (a) the development of REDCap database for study measures and materials, (b) data management, and (c) statistical analyses.

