Participation status will be tracked for all enrolled child/parent participants, and monthly 'Expectation Reports' indicating outstanding assessments will minimize loss of data. Information (e.g., age, reason for non- participation) from eligible participant who do not consent will only be used in summary form to describe the recruitment process. Team training will include all investigators and staff at the initial team meeting and booster sessions as needed to ensure data collection consistency, quality assurance, and intervention fidelity. The PI will provide study manuals, including scripts with instructions, and lead bi-weekly team meetings to maximize recruitment, fidelity, and safety. Questionnaires will be

electronically administered in a standard order with written instructions. Study coordinator or research assistant help will be available in-person to clarify instructions to participants and answer any questions about items. [name] will develop scoring programs and score all measures. Item ranges, and missing and unusual values, will be double-checked.

**Statistical Analysis.** Analysis of the feasibility and preliminary effects of human-animal interactions (HAI) on child and parent stress, depression, anxiety, and quality of life will be conducted using SPSS and STATA statistical software. Descriptive statistical and graphical methods will be used to summarize and visualize patterns in the study outcome data distributions at each time of assessment. Simple group comparisons of participation and retention (e.g., differences in demographic, clinical characteristics) will be conducted using Chi-Square tests of independence and Mann-Whitney tests. Reliable change indices (RCI) will provide the critical foundation for summarizing and analyzing overall efficacy, as well as characteristics of the participants most likely to benefit from HAI in future work. While effect sizes will be more important than statistical significance in this feasibility study, all tests of statistical significance will maintain a maximum  $p < .05$ .

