**Table 3. Study Timeline**

Study Timeline	Year 1				Year 2			
	1	2	3	4	1	2	3	4
Hiring/training personnel, IRB approvals, database	■	■						
Enrolling participants		■	■	■	■	■		
Data collection		■	■	■	■	■	■	
Data analysis								■
Knowledge dissemination and future grant development								■

**Summary, Limitations, and Future Directions:** This pilot/exploratory study will evaluate feasibility, safety, and preliminary efficacy using HAI with children diagnosed with a LTC, but is not generalizable beyond children with advanced cancer. Clear strengths of this proposal include 1) inclusion of children, parents, and canines; 2) qualitative (video recordings, interviews) and quantitative (surveys, physiologic measures) data; 3) use of both established and innovative measures with this population, and 5) expertise of investigators. Collection of physiologic, survey, and observational data will provide a rich view of the experiences of HAI from viewpoints of children with cancer, parents, and animal handlers. This novel design with multiple methods will begin to fill a gap in the literature related to HAI with children with advanced cancer and will lead to future larger studies with other LTC. Infrastructure, institutional support, physical resources and a collaborative research team with established funding history ensure successful completion.

The proposed sample size in this study reflects the number of participants that can reasonably be recruited and followed in this very vulnerable population. The focus will be on generating reliable estimates of characteristics of children and parents who benefit most from this intervention. The subsequent grant will involve multiple sites with English and Spanish-speaking populations and preliminary conversations with several large children’s hospitals are ongoing and yielding positive responses.

**Dissemination:** Results will be disseminated through at least 3 presentations at professional conferences, such as the American Academy of Hospice and Palliative Medicine and Hospice Palliative Nurses Association Annual Assembly, International Congress on Palliative Care, Society of Pediatric Psychology, National State of the Science Congress on Nursing

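### Who benefits most is to be judged from reliable change in a single arm with no stated handling of the baseline score, so a high baseline score will tend to look predictive even if HAI does nothing

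*Combined protocol and SAP*

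**What the plan says.** The Statistical Analysis section makes RCIs the main basis for judging overall efficacy and for identifying the "characteristics of the participants most likely to benefit from HAI in future work". The Summary, Limitations, and Future Directions section gives the question first place: "The focus will be on generating reliable estimates of characteristics of children and parents who benefit most from this intervention".

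The design is a single arm. The Overview says: "Children and parent dyads will receive HAI intervention and complete measures of anxiety, depression, worry, pain and QoL at baseline, 4 weeks", and again at 8 weeks. Outcome surveys are therefore taken once before HAI. Entry depends on disease and not on symptoms: children must be "diagnosed with advanced cancer as defined by any stage of relapsed, recurrent or refractory cancer", with no minimum anxiety, depression or QoL score. Table 2 lists state anxiety as "20 items/20-80; Clinical significance 39-40", measured at all three times; the trait form is completed at baseline only.

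The plan gives no RCI formula, reliability coefficient, cut-off or model for predictors of reliable change. The only group comparisons it names, which "will be conducted using Chi-Square tests of independence and Mann-Whitney tests", concern participation and retention. Neither baseline adjustment nor regression to the mean is mentioned.

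**The concern.** An RCI in its usual form is the baseline score minus the follow-up score, divided by a measure of error. The baseline score is thus part of the quantity that defines benefit. A child who scores unusually high on the baseline day will tend to score lower later for that reason alone. A child who scores low has little room to improve above the floor of 20. With no symptom threshold at entry, both kinds of child should be in the sample.

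This differs from the general problem that a single arm cannot estimate an overall effect. Even if the overall result is labelled preliminary, the ranking of children within the sample by apparent benefit is distorted by construction. That ranking is what the Summary calls the focus. What is at stake is a profile of likely responders, meant to inform later work, that would appear with an inert intervention.

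**Working it through.** The plan states no figure on this point to reproduce.

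**Inputs from the documents.** 30 children (Eligibility Criteria and Recruitment); Cronbach's alpha of .82 to .87 for the child anxiety scale (Measures, Aim 2); significance level .05 (Statistical Analysis), taken here as two-sided.

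**Assumptions.** No HAI effect and no mean change; equal SDs and normal scores at both times; the usual RCI with a 1.96 cut-off and alpha as its reliability. The 8-week stability r (correlation of baseline with week 8) is not in the documents. It is varied over 0.4 to 0.7, plus the limiting case r = alpha.

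**Step 1: baseline score against improvement.** Let X be baseline and Y follow-up, each with SD 1, and D = X − Y. Then cov(X, D) = 1 − r and var(D) = 2(1 − r), so corr(X, D) = (1 − r)/sqrt(2(1 − r)) = sqrt((1 − r)/2).

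| r | 0.4 | 0.5 | 0.6 | 0.7 | 0.82 | 0.87 |
|---|---|---|---|---|---|---|
| corr(X, D) | 0.55 | 0.50 | 0.45 | 0.39 | 0.30 | 0.26 |

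**Step 2: the responder class.** The threshold is 1.96 × sqrt(2(1 − alpha)): 1.96 × 0.600 = 1.18 SD at .82 and 1.96 × 0.510 = 1.00 SD at .87. Simulated percentages reliably improved with no effect, for children above v below the mean baseline score:

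| r | alpha .82 | alpha .87 |
|---|---|---|
| 0.4 | 24% v 5% | 30% v 7% |
| 0.5 | 20% v 4% | 25% v 6% |
| 0.7 | 10% v 3% | 15% v 5% |
| equal to alpha | 3.8% v 1.2% | 3.7% v 1.4% |

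By thirds of the baseline score, for r from 0.4 to 0.7, it is 12%-36% in the top third against 2%-4% in the bottom third.

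**Step 3: significance at n = 30 with no effect.** Baseline tested against continuous change is significant in 90%, 83% and 58% of trials at r = 0.4, 0.5 and 0.7, and in 28%-38% if r = alpha. For the yes/no RCI compared by Mann-Whitney, the rates are 44%-51%, 33%-40%, 13%-18% and about 2%.

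**Step 4: other characteristics.** Let a characteristic correlate c1 with baseline and c2 with follow-up when HAI does nothing. Its unadjusted covariance with improvement is c1 − c2. Its baseline-adjusted slope on improvement is (r·c1 − c2)/(1 − c1²). Take c1 = 0.5.

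- *Linked to the observed baseline score, stable and transient parts alike* (c2 = 0.5r). Unadjusted correlation with improvement is 0.5 × sqrt((1 − r)/2), or 0.27 at r = 0.4 and 0.13 at r = 0.87; falsely significant in 33% down to 10% of trials. Adjusted slope 0; about 5%.
- *Linked only through the stable level* (c2 = 0.5). Unadjusted 0; about 5%. Adjusted slope −0.5(1 − r)/0.75: −0.40 at r = 0.4, −0.20 at 0.7, −0.09 at 0.87. After adjustment it is falsely significant in about 53%, 38% and 25% of trials at r = 0.4, 0.55 and 0.7.
- *Linked only to that day's transient part* (c2 = 0). Unadjusted covariance 0.5; adjusted slope 0.5r/0.75, or +0.27 at r = 0.4 and +0.47 at 0.7. Both analyses point to benefit although there is none.

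**The case against.** The strongest reply is that the plan is silent, not wrong. It does not say that the baseline score will be ignored. The RCI variant rests on cited references not available here, and no section names baseline state anxiety as a candidate predictor. The characteristics on the Family Demographic Form (age, race, gender, diagnosis, family members, pet ownership) are mostly stable. The study calls itself a pilot and ranks effect sizes above significance. With a yes/no RCI and stability as high as alpha, a false significant finding for baseline is rare (about 2%).

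Much of this stands, and it limits the point. Four stronger readings are tempting but not supported:

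- *That anything correlated with baseline anxiety will look predictive.* Step 4 shows that a characteristic tied only to the stable level does not.
- *That adjusting for baseline cures the problem.* It does so only for characteristics that act through the observed score. For stable ones it raises false findings from about 5% to 25%-53%. Trait anxiety, meant to be stable, is an obvious risk.
- *That the 90% to 58% rates describe the planned analysis.* They are for continuous change; the plan does not fix the analysis, and the yes/no rates are lower.
- *That the result would set eligibility for the next trial.* The Summary describes the next grant only as multi-site with English and Spanish speakers.

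The reply does not remove the core. How baseline is handled is unstated for the study's declared focus. Preferring effect sizes does not help either: the expected spurious correlation is positive at every r below 1, and is still 0.26 to 0.30 when r equals alpha.

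**Conclusion.** The point holds in limited form and should be addressed. With one arm, one baseline survey and benefit defined by reliable change, a high baseline anxiety score will tend to look like a predictor of improved anxiety when HAI does nothing; for QoL, where a higher score is better, the mirror image applies. The expected correlation is 0.55 to 0.39 for stability of 0.4 to 0.7, and 0.30 to 0.26 if stability equals the quoted alpha. Characteristics that share the baseline day's transient part, such as other state measures taken that day, inherit some of this. Characteristics tied only to the stable level do not.

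The size depends on the assumed stability, equal variances, and the usual RCI with a 1.96 cut-off. The direction needs only equal variances and stability below 1. That no baseline handling is intended is inferred from silence; the supportable statement is that none is specified.

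**What to change.** Add one paragraph to the Statistical Analysis section:

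1. State the RCI formula, reliability coefficient and cut-off, so that the unadjusted analysis is defined.
2. State that the baseline level of the same measure, or being above the 39-40 cut-off, will not be reported as a characteristic of benefit, because this design cannot separate it from regression to the mean.
3. For every other characteristic, present two analyses side by side: unadjusted (RCI or change), and follow-up score regressed on the characteristic plus the baseline score of the same measure. Call a characteristic supported only if both agree in direction and conclusion; otherwise report it as unresolved.
4. Apply the same two-way presentation to the trait form.
5. Note that agreement is necessary but not sufficient: a state measure taken on the baseline day can pass both by sharing that day's transient part (Step 4, third case), and should be reported with that caveat.

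The cost is slightly more analysis and text; all data are already to be collected. The downside is that some characteristics, perhaps including real ones, will be left unresolved.

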**Table 3. Study Timeline**

Study Timeline	Year 1				Year 2			
	1	2	3	4	1	2	3	4
Hiring/training personnel, IRB approvals, database	■	■						
Enrolling participants		■	■	■	■	■		
Data collection		■	■	■	■	■	■	
Data analysis								■
Knowledge dissemination and future grant development								■

**Summary, Limitations, and Future Directions:** This pilot/exploratory study will evaluate feasibility, safety, and preliminary efficacy using HAI with children diagnosed with a LTC, but is not generalizable beyond children with advanced cancer. Clear strengths of this proposal include 1) inclusion of children, parents, and canines; 2) qualitative (video recordings, interviews) and quantitative (surveys, physiologic measures) data; 3) use of both established and innovative measures with this population, and 5) expertise of investigators. Collection of physiologic, survey, and observational data will provide a rich view of the experiences of HAI from viewpoints of children with cancer, parents, and animal handlers. This novel design with multiple methods will begin to fill a gap in the literature related to HAI with children with advanced cancer and will lead to future larger studies with other LTC. Infrastructure, institutional support, physical resources and a collaborative research team with established funding history ensure successful completion.

The proposed sample size in this study reflects the number of participants that can reasonably be recruited and followed in this very vulnerable population. The focus will be on generating reliable estimates of characteristics of children and parents who benefit most from this intervention. The subsequent grant will involve multiple sites with English and Spanish-speaking populations and preliminary conversations with several large children’s hospitals are ongoing and yielding positive responses.

**Dissemination:** Results will be disseminated through at least 3 presentations at professional conferences, such as the American Academy of Hospice and Palliative Medicine and Hospice Palliative Nurses Association Annual Assembly, International Congress on Palliative Care, Society of Pediatric Psychology, National State of the Science Congress on Nursing

Research, and Oncology Nursing Society National Conference on Cancer Nursing Research. Our main form of dissemination will be through several peer-reviewed publications in multidisciplinary journals and will include manuscripts related to: (1) outcomes of childhood anxiety, depression, worry, pain, and QoL (2) parent outcomes of anxiety, stress, and quality of life, and (3) participants' qualitative reports on their experiences with HAI.

### **Data Safety and Monitoring Plan:**

**A. Monitoring Entity or Who Will Monitor the Study:** The data and safety monitoring plan will follow NIH policy guidance. Based on this study being minimal risk and conducted at a single site, a Safety Monitoring Committee (SMC) consisting of at least two (2) experts who are not co-investigators or consultants on this study will be established at Vanderbilt University at the beginning of this research. SMC membership will follow NIH policy. The SMC will serve as an independent advisory board to both the PI and to the NICHD Director. The SMC will oversee the activities related to implementing the study to ensure patient safety, conformance to the study protocol, overall performance of study components, and integrity of the data being collected. SMC members will not have close current or recent affiliations with the study, will not have been directly involved in protocol development, nor supervise persons who are so involved. We will make every effort to include an independent investigator and biostatistician. As soon as possible after each SMC meeting, but within 20 days following each SMC meeting, the SMC will provide the PI with a copy to provide to the NICHD Director or designee, a written recommendation along with justification related to continuing, changing, or terminating the study. The PI will be responsible for submitting any necessary reports to the NICHD.

### **B. Procedures for:**

**B1 a) Monitoring study safety to include monitoring schedule:** The SMC will meet a minimum of once a year to review study progress through informal evaluation of existing data. For each SMC meeting, reports will be prepared and provided to SMC members by the PI. Data will be provided in a manner to protect the confidentiality of subjects. The SMC will prepare an annual safety report, summarizing the efforts and findings of the Committee.

**B1 b) Auditing selected cases for compliance with IRB requirements:** The SMC will annually audit selected cases for IRB compliance with study procedures.

**B1 c) Conformance with informed consent requirements:** The SMC will annually audit consent and assent documents and study conformance with related requirements.

**B1 d) Verification of source documents:** The SMC will verify that study record-keeping includes documenting the existence of the subject to substantiate data collection integrity.

**B1 e) Investigator compliance:** The SMC will annually review all study investigators' compliance with human safety training.

**B2) Minimizing research-associated risk:** The SMC will monitor study data for effectiveness and safety to protect participants from exposure to unreasonable or unnecessary research risks. SMC members will review interim data in the context of the most recent scientific literature, and ensure that the study does not continue beyond the point when the study objectives have been met and a clinically meaningful answer of importance to the scientific community and the public has been obtained.

**B3) Protecting the confidentiality of participant data:** The SMC will review study plans for and establish specific guidelines for data and safety monitoring, including confidentiality of participant data (e.g., location of data storage.)

**C. Procedures for Identifying, Reviewing, and Reporting Adverse Events and Unanticipated Problems to the IRB and NINR.** Any adverse events occurring during the course of this study will be collected, documented and reported by the PI ([name]) to the SMC, along with reporting to the NICHD and institutional review boards as required. As soon as possible after each SMC meeting but within 20 business days following each SMC meeting, the SMC will provide the PI and the NICHD with a statement, where appropriate, concerning the impact of the study of individually observed or cumulative adverse events. Although not anticipated, if any 1 event is identified that may have caused any type of harm to a participant, study accrual will be immediately halted until the study team and SMC can review the event and determine if any study procedures need to be revised. Study accrual will only resume after review of study protocol has been completed and any recommended revisions made as suggested by the SMC.

**D. For Multi-Site Studies, Procedures to Ensure Compliance with Monitoring Plan and Reporting Requirements across Study Sites.** N/A - as this is a single site study.

**E. An Assessment of External Factors or Relevant Information (i.e., Developments in Literature, Results of Related Studies) that May have Impact of Participant Safety or on Ethics for Research Study.** The SMC will review published reports of related studies submitted by the study investigators or SMC members to determine any external factors which may impact participant safety or ethics for our study. The SMC will determine whether the monitored study needs to be changed or terminated.

**F. The Advanced Plans for Interim and/or Futility Analysis:** Given the low risk of any negative impact of the intervention, as well as the considerable variability commonly seen in study outcomes, we will not reduce study statistical power by including an interim or futility analysis. Subsequent research will be greatly benefited by the proposed analysis that will make use of the full sample recruited in this study.

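### Does the monitoring committee's duty to stop once the study has its answer conflict with the decision to hold no interim analysis?

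*Combined protocol and SAP*

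**What the plan says.** All the relevant text is in the Data Safety and Monitoring Plan.

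- **Section B2** opens: "The SMC will monitor study data for effectiveness and safety", and gives the purpose as shielding participants from unreasonable or unnecessary research risk. It adds: "SMC members will review interim data in the context of the most recent scientific literature". The SMC is then to "ensure that the study does not continue beyond the point when the study objectives have been met and a clinically meaningful answer" has been obtained. No outcome, timing or threshold is named.
- **Section B1 a** sets at least one meeting a year, at which the SMC is to "review study progress through informal evaluation of existing data".
- **Section A** makes the committee advisory: "The SMC will serve as an independent advisory board to both the PI and to the NICHD Director". After each meeting it issues "a written recommendation along with justification related to continuing, changing, or terminating the study".
- **Section F** states that "we will not reduce study statistical power by including an interim or futility analysis", and says that later research will benefit from "the proposed analysis that will make use of the full sample recruited in this study".

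Sections B2 and F do not refer to each other, and the Statistical Analysis section does not mention interim review.

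**The concern.** Section B2 can be read as a mandate to stop for benefit, and section A supplies the route through the written recommendation after each meeting. Section F gives up interim analysis to protect power and keep the full sample. An informal stop on good early results would defeat both aims as surely as a formal one.

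The stake is the study's main product. The Statistical Analysis section ranks effect sizes above significance tests, and the Summary, Limitations, and Future Directions section puts the emphasis on reliable estimates. Stopping on favourable early data would leave fewer children and estimates that tend to be too high, and those estimates are meant to inform a larger multi-site study.

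**Working it through.** **1. Do the passages contradict each other?**

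- Section F concerns planned interim and futility analyses and says there will be none. Section B1 a describes an informal look at accumulating data. A committee can do the second without the first.
- Section B2's stopping clause requires that the objectives be met *and* that a clinically meaningful answer be in hand. Under Measures, Aim 1 covers modifications, recruitment estimates and barriers, fidelity and safety. Aim 2 covers quality of life, anxiety, depression, worry and pain in children, and stress and anxiety in caregivers. Recruitment estimates in particular need recruitment to run its course.
- Harm is handled separately in section C and external evidence in section E. Neither depends on how sections B2 and F are read together.

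What remains is a tension with section F's reasons, not with its rule.

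**2. What would an early stop cost if it happened?**

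Inputs:

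- Completers (Table 1): 32 × 1.5 = 48 eligible; 48 × 0.85 = 40.8, shown as 40; 40 × 0.75 = 30. The plan's figure of 30 reproduces.
- Enrolment length: 18 months (Eligibility Criteria and Recruitment) or five quarters, 15 months (Table 3), starting after the first 3 months (Table 3).
- Participation: 8 weeks, about 2 months.
- Assumptions: one SMC meeting at month 12 (section B1 a gives only a yearly minimum) and even accrual.

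Children enrolled early enough to have finished by month 12 come from 12 − 3 − 2 = 7 months of enrolment:

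- 30 × 7/18 = 11.7, about 12
- 30 × 7/15 = 14

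If only accrual stopped and children already enrolled finished, 12 − 3 = 9 months would count: 30 × 9/18 = 15 or 30 × 9/15 = 18.

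The 95% confidence interval half-width for a mean change, in SDs of the change, is t(0.975, n − 1)/√n:

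| n | Half-width | Ratio to n = 30 |
|---|---|---|
| 12 | 0.635 | 1.70 |
| 14 | 0.577 | 1.55 |
| 15 | 0.554 | 1.48 |
| 18 | 0.497 | 1.33 |
| 30 | 0.373 | 1 |

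The 18-month cases (12 and 15) combine Table 3's start with a longer accrual period that would run to month 21, beyond Table 3's enrolment window. The cases of 14 and 18 follow Table 3 alone.

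**3. How many chances are there?** Table 3 ends enrolment after month 18 and data collection after month 21. On the minimum yearly schedule, with meetings at months 12 and 24, only the first could shorten the study.

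**4. Can the overestimation be sized?** Not from the documents. It depends on the stopping rule, and the plan has none. Assuming a significance threshold on one outcome would describe a different trial, since section B2 requires the study's objectives as a whole to be met.

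**The case for a change.** The strongest case for a change is that the stopping clause turns on met objectives and a meaningful answer, not on harm. Calling the review informal does not remove that duty or give it a criterion. Section B3 asks the SMC to establish monitoring guidelines, but it sits under a confidentiality heading and does not mention effectiveness. One sentence barring a stop for apparent effectiveness would apply the sponsor's own decision in section F at almost no cost.

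Much of this stands. The wording is uncoordinated, no passage forbids such a recommendation, and section B3 does not settle the matter. The added sentence, however, gains little. It would leave the duty not to continue past the answer in place beside a bar on acting on it, so the tension would move inside section B2. It would also limit in advance what an independent advisory committee may recommend, which is debatable in its own right. The part of it that ties outcome data to judging risk would largely repeat the purpose section B2 already states.

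**Conclusion.** No change is needed. This is a gap in wording that a committee and its analysts can fill sensibly: the SMC reviews accumulating data informally to protect participants, no formal interim test is run, and the analysis uses the full sample.

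If a stop were recommended and accepted at month 12, the half-width would be 0.58 to 0.64 SD among those who had finished, or 0.50 to 0.55 SD if enrolled children completed, against 0.37 SD at 30. These figures rest on even accrual, a single meeting at month 12 and 30 completers in all. They are conditional on an event that the two-part condition, the breadth of the objectives and the SMC's advisory status make very unlikely. No probability of that event can be derived from the plan, and no effect on conduct or results has been shown.
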